7.2 Adjustments for Covariates

Indicator variables for the study stratification of site will be included as covariates in most efficacy analyses performed for this study (details in section 9). Additionally, demographic and baseline characteristics for subjects and clinicians will be compared between study arms using analysis of covariance techniques for continuous measures, Mantel-Haenszel mean score test using standardized midrank scores for ordinal measures, and Cochran Mantel-Haenszel chi-square tests for general association for categorical measures. If sample sizes allow, these analyses will control for the study stratification factors. If these analyses suggest that substantial differences exist among arms, the use as covariates of these parameters on which the arms differ will be explored in secondary exploratory analyses of the efficacy data.

7.3 Handling of Dropouts and Missing Data

Standard procedures will be used to ensure that data are as complete and accurate as possible. The study was designed to obtain as much follow-up data as possible on all randomized subjects. In analyses, a full accounting will be made for all data items. Generally, missing data will initially be treated as randomly missing (either missing at random (MAR) or missing completely at random (MCAR) as appropriate for the analytic approach) with no data imputation. Because we anticipate that the amount of missing data will be minimal, we will use straightforward multiple imputation procedures based on baseline covariates and treatment group to assess sensitivity to the random missingness assumption for both primary and secondary analyses.

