The primary aim of SUPeR was to determine whether treatment success in women with symptomatic uterovaginal prolapse undergoing transvaginal mesh augmented hysteropexy differs in women undergoing vaginal hysterectomy and native tissue cuff suspension at time points through 3 years. The study was designed with a survival analysis approach with 36 month follow-up after last enrollment with an expected 2 year enrollment period. SUPeR randomization began in April 2013, enrollment ended in October 2014, and the last surgery (randomization) was performed in January 2015. All subjects reached 3 year follow-up in March 2018. Retention in this time period was excellent; three year primary outcome data was available for 96% of the participants. Some participants have reached the 5 year follow-up time point and have been unmasked.

What has become apparent with this excellent follow-up is that the SUPeR cohort represents a unique opportunity to understand the longer term efficacy and safety outcomes of a native tissue repair and a mesh hysteropexy. There are no studies in the literature with such outstanding long-term follow-up over an extended period of time. The current 96% retention rate underscores how readily participants accept the evaluations that have been performed in this study.

Proposed Extension of Study

This amendment proposes to continue to follow the subjects in this study who have not undergone reoperation for prolapse until reoperation for prolapse is reported, 10 years of follow-up is completed, or until participant retention in this study falls below 60%. To decrease subject burden, the frequency of study visits will be reduced from every 6 months to annually from the date of surgery. A reduction of select secondary patient reported outcome measures that are unlikely to provide interesting data during this 5-10 year time period is proposed.

The annual follow-up visits for year 6 could begin as early as April 2019 when our first subject reaches the 6 year mark. The table below represents the abbreviated outcome measures that will be collected at each annual visit.

Measure	6 years	7 years	8 years	9 years	10 years
POPQ	X	X	X	X	X
AE review	X	X	X	X	X
Exam for mesh exposure	X	X	X	X	X
PFDI-20 (includes POPDI-6, CRADI-8, UDI-6)	X	X	X	X	X

Confidential Please Do Not Copy

Measure	6 years	7 years	8 years	9 years	10 years
PFIQ	X	X	X	X	X
PGI-I	X	X	X	X	X
ISI	X	X	X	X	X
PISQ-IR	X	X	X	X	X

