6 SAMPLE SIZE DETERMINATION

This study is designed to compare the relative effectiveness of two transvaginal apical suspension strategies for uterovaginal prolapse: a mesh augmented hysteropexy vs. vaginal hysterectomy and uterosacral ligament suspension. Power and sample size calculations were generated to determine the sample size needed to test for treatment difference favoring the mesh augmented strategy (i.e., a superiority trial) across the study arms for a variety of assumptions about effect size and study followup time. For all power analyses, we assumed that failure in both arms follows an exponential survival model and that the native tissue repair has a success rate of 80% at 24 months. This 80% calculation is based on an assumed 85% anatomic success rate for uterosacral ligament suspension (Table 2) and an additional 5% failure rate based on symptom failure. In the only published Uphold series there is a 98 % 12 month anatomic success rate.32 Although no 2-year outcome data are available for the UPHOLD procedure, under an assumption of a constant hazard, the 1-year success rate of 98% yields an estimated 2-year anatomic success rate of 96%; combining this estimate with a similar 5% rate for symptom failure yields a 91% composite (anatomic and symptom) success rate. All analyses also assumed that statistical tests would be conducted with a Type I error rate of 0.05 with no adjustment for multiple comparisons. Sample size estimates assumed that the 2-year success rate in the meshaugmented arm is in the range of 90% to 93% at 24 months (note that this represents a hazard ratio in the range of 0.33 to 0.47 under the assumed exponential survival model), that the enrollment time for the study is 2 years, the loss-to-follow-up on both arms is no more than 5% per year, and the total study duration from last participant enrolled to stopping the study for final analysis is 36 months with one interim analyses for efficacy when the last participant reaches the 24-month follow-up. Table 6 provides estimates of the power for the different assumptions for total sample sizes in the range of 160 to 300 participants.

Total Sample Size	Power as a Function of 2-Year Effect Size—with base 2-Year Success of 80% and 36-Month Follow-up after last enrollment and a 2-year Enrollment Period						
	∆= 0.10 HR=0.472	Δ=0.11 HR=0.423	Δ=0.12 HR=0.374	∆=0.13 HR=0.325			
160	0.87	0.93	0.96	0.99			
180	0.89	0.95	0.98	0.99			
200	0.92	0.96	0.99	>0.99			

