7.5 Masked Data Review

A masked data review is planned prior to the data lock once all study participants reach the 36-month visit. All eligibility, protocol deviation, and visit window data will be reviewed by the protocol team in a masked fashion. Details of the results from the masked review will be documented in a SAP addendum once the review is complete. Specific items to be addressed in the masked data review are:

- Reason for study withdrawal and missed visits (adverse event, death, patient moved, lack of efficacy, etc. to determine whether the event was likely to be missing at random or informatively missing).
- Characterization of individual failures (by time and reason for failure) to ascertain failure time for the primary outcome and failure across time span for secondary analyses related to changing status of anatomical prolapse failure and bulge symptoms.
- Review of deviations (excluding missed/incomplete visits/assessments)
- Summary of interoperative complications from C3 in Form 9. The summary will include a count and percentage for each of the complications listed in the table as well as a table that shows the percentage of individuals have different numbers of complications. The summary will also include the distribution of Dindo scores, and the listing of complications that generated the Dindo scores.
- Duration of catheterization (categorical measure of none, less than 1 week, 1 to 2 weeks, 2 to 4 weeks and greater than 4 weeks).
- Visit windows
 - All baseline data will be used regardless of time of collection so long as the data were collected prior to treatment initiation. If more than one assessment of an outcome is reported within a visit window, the earliest assessment will be used. If no assessments are available for a visit (e.g., assessments were completed but none within study window), then an out of window assessment will be used for that visit so long as the out of window assessment does not also fall into a window for a different study visit. Rules for classifying visit membership for out of window assessments will be further determined as part of a review by the protocol team using masked data.
- UTI classification

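### The planned multiple imputation assumes missing at random, so it cannot show whether the results survive informative dropout, and no other analysis in the plan does

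*SAP*

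**What the plan says.** SAP Section 7.3 sets the default: "Generally, missing data will initially be treated as randomly missing". The same sentence explains the term: "either missing at random (MAR) or missing completely at random (MCAR) as appropriate for the analytic approach) with no data imputation". The sensitivity analysis follows. It opens "Because we anticipate that the amount of missing data will be minimal", continues "we will use straightforward multiple imputation procedures based on baseline covariates and treatment group to assess sensitivity to the random missingness assumption", and applies "for both primary and secondary analyses".

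SAP Section 7.5 has the protocol team review reasons for withdrawal and missed visits, masked to arm, "to determine whether the event was likely to be missing at random or informatively missing". Lack of efficacy is among the example reasons. Results of the review are to go into a SAP addendum, which is not among the documents available here.

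Two statements bear on how much is missing. The design assumes that "the loss-to-follow-up on both arms is no more than 5% per year" (SAP Section 6). The extension amendment reports that "three year primary outcome data was available for 96% of the participants" (Protocol section U, Background).

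The only other imputation is a sensitivity analysis for cost-effectiveness (Protocol section M, Secondary Aim 4; SAP Section 9.4.5). It adds no departure from MAR. Neither document plans a delta adjustment, tipping point, reference-based imputation, pattern-mixture or selection model, or worst-case bound.

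**The concern.** A sensitivity analysis should relax the assumption it examines. Imputation of this kind fills in each missing outcome from women who were observed and who share the same arm and baseline values. If women stop attending because the repair is failing, the imputed values inherit the bias already present in the observed data. Agreement between the main and imputed results would then say nothing about informative dropout, although a reader could take it as reassurance.

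The plan itself treats informative missingness as possible, since Section 7.5 sets out to identify it. The SAP text stops at the classification.

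**Working it through.** The plan gives no figure on this point, so there is none to reproduce. The check has four steps.

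**1. What the imputation can relax.**

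| Analysis | Conditions on | What the planned imputation adds |
|---|---|---|
| Piecewise exponential model, primary (SAP 9.3) | arm, site, failure status, time at risk | possibly more baseline covariates; still MAR |
| Generalized log-rank (9.3), exact tests at visits (9.3), chi-square (9.4.2) | arm | a check of MCAR against MAR |
| GEE for binary outcomes (9.4.3) | arm, visit, site; generally needs MCAR given these | a check of MCAR against MAR |
| Linear mixed models (9.4.1) | arm, visit, site, earlier post-operative values | still MAR, and omits the earlier values |

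No row reaches MNAR.

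**2. How much is missing.** Four per cent of 175 women (the total in the SAP Section 17 shells) is 0.04 × 175 = 7.0; of 180 it is 7.2. At 5% per year for three years, 1 − 0.95³ = 14.3%, which is 25.0 of 175 or 25.7 of 180.

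**3. Whether the planned imputation would reveal informative loss.** Design rates carried to 36 months under the exponential model give failure of 1 − 0.80^1.5 = 28.4% (native tissue) and 1 − 0.90^1.5 = 14.6% (mesh), a difference of −13.8 points. This was simulated as a binary outcome (1,500 trials, 180 women, 20 imputations, logistic imputation from arm and one baseline covariate). Two assumptions are not from the documents: the covariate has a log-odds ratio of 0.5 and, in the MNAR rows, mesh-arm failures are 5 times as likely to be missing as successes. Mean differences, in points:

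| Missing | Mechanism | Full data | Complete case | Planned-type imputation |
|---|---|---|---|---|
| 4% | MAR | −13.6 | −13.6 | −13.6 |
| 4% | MNAR | −14.1 | −15.4 | −15.4 |
| 14.3% | MAR | −13.9 | −13.8 | −13.8 |
| 14.3% | MNAR | −13.8 | −19.1 | −18.9 |

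Under MNAR the imputed result stays with the biased complete-case result.

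**4. What a shifted analysis would show.** Take 90 per arm, p = 0.1462, odds o = p/(1 − p) = 0.1712, and missing fraction m in each arm. Multiplying the odds of failure among missing mesh women by r gives q = r·o/(1 + r·o) and moves the difference by m(q − p).

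- r = 2, 3, 5 gives q = 0.255, 0.339, 0.461.
- m = 4/90: differences of −13.3, −13.0, −12.4 points.
- m = 13/90: differences of −12.3, −11.0, −9.3 points.
- Worst and best case, (1 − m)(−13.83) ± 100m: −8.8 and −17.7 for m = 4/90; +2.6 and −26.3 for m = 13/90.

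The effect on significance was simulated with 175 women, success of 80% v 90% at 24 months, 6-month visits, a grouped log-rank test, 10 imputations and 800 trials per setting. The hazard after loss was multiplied by 3 or 6. Share of significant results that stop being significant:

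| Women lost | Shift | ×3 | ×6 |
|---|---|---|---|
| about 6 | mesh arm only | 8% | 16% |
| about 6 | both arms | 3% | 6% |
| about 22 | mesh arm only | 26% | 52% |
| about 22 | both arms | 5% | 8% |

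With no shift, imputation noise alone removed 1% (about 6 lost) and 3% (about 22 lost) in 600 trials per setting. A separate mesh-only simulation gave 6% and 12% (about 6 lost) and 18% and 41% (about 22 lost), with noise of 3% and 6%, so these sizes are approximate. The counts of 6 and 22 are below the 7 and 25 of step 2 because some women fail before they are lost.

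**The case against.** The case for the plan is substantial, and most of it stands.

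- **The imputation has a use.** Section 7.3 covers MCAR as well as MAR. A reader might infer that the imputation merely repeats the main analysis. That is not so for the GEE, chi-square, exact and generalized log-rank analyses.
- **Information used.** A reader might infer that the imputation uses less information than every main analysis. This is shown only for the mixed models. The primary model does not take POPQ values or bulge answers as predictors, and baseline imputation could condition on more than it does.
- **The masked review.** A reader might infer that the classification leads nowhere. The addendum could contain an analysis, and Section 7.3 says only how missing data are treated initially. What can be said is that the SAP text makes no link.
- **Claimed robustness.** Nowhere do the documents say the results will be called robust to informative dropout. That is a risk in interpretation.
- **Design protections.** Failure is absorbing in the primary analysis (SAP 9.3), so a woman seen to fail before she leaves is already counted. Retreated women stay in follow-up (Protocol section K), and coordinators pursue out-of-window visits (SAP 7.9). What remains is failure after the last attended visit.
- **Direction.** The larger percentages shift the mesh arm alone, and the documents give no reason to expect that asymmetry.
- **Test used.** The significance simulation uses a log-rank test, which SAP 9.3 replaced as primary. The piecewise exponential model also treats censoring as non-informative, so the reasoning carries over, but the percentages may not carry over exactly.

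None of this supplies an MNAR analysis.

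**Conclusion.** The point holds in a limited form. The planned imputation cannot examine departure from MAR towards informative dropout, and neither document specifies an analysis that does.

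At 36 months the consequence is probably modest. With about 4 women missing per arm, a fivefold odds shift moves the difference by 1.4 points (−13.8 to −12.4), and even the worst case keeps its sign. It could be larger at the planned 5% per year loss, where the worst case reverses the sign, or later. A 60-month efficacy analysis is planned (Protocol section O). The extension expects about 5% fewer participants per year, through withdrawal or reoperation, and will reuse methods consistent with those at 3 and 5 years (Protocol section U).

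The multipliers, the fivefold missingness and the direction of shift are assumptions, and the event rates are design values. A reader might infer that the primary conclusion is unsafe or biased; the documents do not support that. No analysis can prove MAR from observed data, so the remedy is to vary the assumption.

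**What to change.** In SAP Section 7.3:

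1. Keep the multiple imputation, and label it as an analysis under MAR.
2. For the primary outcome, add a delta-adjusted imputation of failure after last contact. Multiply the hazard by a prespecified range, varied separately in each arm and in both arms together.
3. Report the tipping point: the multiplier, or pair of multipliers, at which the primary conclusion changes.
4. Apply the shift first to women whom the masked review classed as informatively missing, then to all women lost. If the addendum already contains such an analysis, cross-refer to it.
5. For secondary longitudinal outcomes, include earlier post-operative values in the imputation model.

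The cost is SAP wording and one extra analysis on existing data, with no new visits or data collection. If the arms have already been unmasked, fix and date the range before running the analysis and label it as added. The downside is a robustness statement that may be less favourable than the planned imputation would give.

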The first two sections below describe a modified analytic approach that treat participants in a manner consistent with the original analysis design in that study participants that meet the criteria for treatment failure a remain treatment failures until they are lost to follow-up or the study ends. The proposed model-based and nonparametric analytic methods address interval censoring and non-proportional hazards in the assessment of the study's primary hypothesis. The model-based approach will serve as the primary analytic method for testing the efficacy of the two strategies for uterovaginal prolapse as it can control for study design and potentially confounding variables, while the nonparametric method will serve a confirmatory role, particularly in the masked analysis as detailed below. The third section focuses on modeling recurrent events to better understand the impact of the interventions over time. The analytic methods for estimating survival curves will first be conducted in a blinded fashion on all subjects, ignoring treatment assignment as a part of a masked analysis, then comparing subjects randomized their interventions in an unmasked analysis.

Model-based analysis:

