The GLMM of the PWE survival model will be is specified with (1) a Poisson distribution, (2) an offset variable denoting the logarithm of the exposure time during a given period, and (3) subjectspecific random intercepts to incorporate within-subject homogeneity, using the SAS GLIMMIX procedure in SAS STAT version 14.2 (SAS Institute Inc. 2016). The study's follow-up time will be divided into three periods: first, before and up to 12-months; second, 13 months to 30 months; and third, 31 months and beyond. The choice cut points will be evaluated during the masked analysis with a plot of the NPMLE survival function (described below) and adjusted if necessary. As it is possible for subjects to have a right censored treatment failure at the beginning of a period, resulting in an exposure time of zero and a offset variable that is undefined, subjects experiencing a treatment failure at the beginning of a given period will be assigned an exposure time of 0.5 months and an offset variable of log(0.5). The unmasked analysis will use the GLMM specified above to generate an overall test of the failure hazard ratio across the two interventions using a two-sided hypothesis test with an overall type I error rate of 0.05, controlling for the design variables of site the subject was recruited into. Also, the point and interval estimates of 12-, 24- and 36-month treatment failure rates on each intervention arm as well as hazard ratios between the two arms will be provided. Additional models will be used to evaluate potentially confounding variables of subject age and prior prolapse surgery.

Nonparametric analysis:

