9.4 Secondary Efficacy Analysis Methods

9.4.1 General Approach

As outlined in the above sections, the secondary outcome variables comprise a combination of binary, ordinal, and continuous measures that are collected at 6-month intervals through post-operative Month 24 and at either 6- or 12-month intervals thereafter. These outcome measures will be summarized in both tabular and graphical fashion by treatment arm over the full follow-up period, although the focus of the analysis will be on the first 36 months of the post-operative period. We will then use model-based approaches appropriate for the variable type (linear mixed models for continuous variables and GEE extensions of robust Poisson regression models for binary outcomes) to compare the outcomes for the two treatment arms across time.

Because the primary scientific interest for the study is in the trajectories of various the outcomes across time and because information about the patterns of these trajectories is limited, a longitudinal approach incorporating all time points will generally be employed. Specifically, the unit of analysis will be the participant visit, where visits are defined as in Section 4.5 starting 6 months post operatively, and the models will incorporate treatment group, time, and treatment group by time, as well as site, the randomization stratification variable, as fixed effects in the model with time (or visit) will be treated as a categorical variable to incorporate the expected non-linearity of time effects. Participant will be included as a random effect in the linear mixed model with an assumed compound symmetric covariance structure across the post-operative observation period and this same compound symmetric structure will be assumed in the GEE model with observations clustered within participant. The general structure of the SAS code that will be used for the mixed model (using the POPDI-6 as an example) is summarized below.

Proc Mixed data=SUPeR;

WHERE visit le 36; *** Constrains analysis to first 36 months of follow-up;
Class treatment visit center participant;
Model POPDI-6=treatment visit treatment*visit center/solution;
Random participant;
Lsmeans treatment*visit/ pdiff Cl;
Contrast 'POPDI Outcome' treatment 7 -7 treatment*month 111111111-1-1-1-1-1;

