9.4.4 Predictors of Poor Treatment Effect

Two approaches will be utilized to evaluate predictors of poor treatment effect. First a binary outcome of treatment failure over a 36-month post-operative period will be created. Contingency tables and univariate logistic regression models will be used to determine whether this binary outcome is related to the potential predictors of advanced prolapse, age, obesity, smoking, menopausal status, estrogens, primary vs. recurrent prolapse, and physical and functional activity. Any covariates that are related to the outcome measure at a p-value of 0.10 will be utilized in a multivariable logistic regression model to develop an overall predictive model for treatment failure.

The second approach will involve fitting a multivariable complementary log-log model comparable to the model described in the Section 9.3 that includes the covariates described above with any covariates with a p-value of 0.10 or greater retained in the final model.

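### The sensitivity imputation in SAP 7.3 leaves out each woman's post-operative results, which the main models use, and does not say what is imputed for the primary outcome

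*SAP*

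**What the plan says.** SAP 7.3 first treats missing data as missing at random or completely at random, without imputation. It expects little missing data and adds a check: "we will use straightforward multiple imputation procedures based on baseline covariates and treatment group", in order "to assess sensitivity to the random missingness assumption for both primary and secondary analyses". No other section widens the list of predictors. Section 7.5 plans a masked review of reasons for withdrawal and missed visits. Section 9.3 uses imputation only for standard errors and the covariance of the rank statistic. Section 9.4.5 names multiple imputation for costs without listing predictors.

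The main analyses do use post-operative follow-up. In the primary piecewise-exponential model (9.3) each woman contributes her time at risk by period, and women who fail "remain treatment failures until they are lost to follow-up or the study ends". For the secondary outcomes, "a longitudinal approach incorporating all time points will generally be employed" (9.4.1), through mixed models for continuous measures and GEE Poisson models for binary ones.

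Fixed-time failure quantities are also planned. Section 9.3 promises "the point and interval estimates of 12-, 24- and 36-month treatment failure rates on each intervention arm", and 9.4.4 says "First a binary outcome of treatment failure over a 36-month post-operative period will be created". Section 7.3 does not say whether the primary-outcome imputation fills in a visit status, a period indicator or a failure time.

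**The concern.** A sensitivity imputation should condition on at least what the main analysis conditions on. This one adds baseline covariates but drops the woman's own post-operative course, usually the best predictor of her missing value. Missing at random allows dropout to depend on earlier observed scores. An imputation model without those scores is then misspecified even though the assumption under test is true. A disagreement with the main result would say nothing about that assumption, and agreement would be weak reassurance.

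Two further consequences follow:

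- **Binary secondary outcomes.** An unweighted GEE generally needs data missing completely at random, given its covariates. This is where a good imputation would help most, and one based on baseline and arm cannot correct for dropout that depends on an earlier post-operative result.
- **Primary outcome.** Failure is absorbing, so a woman whose 36-month status is unknown was failure-free when last seen. Imputing that status from arm and baseline gives her the arm's whole 36-month risk, which is too high even when loss is entirely non-informative.

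**Working it through.** **Inputs.** From SAP section 6: exponential failure; 24-month success 80% (native tissue) and 91% (mesh, the composite figure); loss of at most 5% per year. From the E-SUPeR amendment in the protocol: three-year primary outcome data for 96%. The calculation treats loss as non-informative and failure as seen up to the time of loss, a simplification of the six-monthly visits.

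**1. The plan's own figure.** Yearly hazard = −ln(S24)/2, so 0.1116 (native) and 0.0472 (mesh). The ratio is ln(0.91)/ln(0.80) = 0.423, as in the SAP's power table.

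**2. Risk for one woman.** Arm-level 36-month failure is 1 − S24^1.5. Given failure-free at 24 months, it is 1 − S24^0.5.

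| | Native | Mesh |
|---|---|---|
| Arm-level 36-month failure | 28.4% | 13.2% |
| Given failure-free at 24 months | 10.6% | 4.6% |

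The arm-level risk is 2.7 to 2.9 times the conditional risk.

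**3. Effect on the arms if 36-month status is imputed from arm, 5% loss per year.** Loss hazard η = −ln(0.95) = 0.0513.

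- Observed failure = λ/(λ+η) × [1 − exp(−3(λ+η))]: 26.5% and 12.2%.
- Completed failure-free = exp(−3(λ+η)): 61.3% and 74.4%.
- Status unknown (the remainder): 12.2% and 13.3%.
- True risk in that group = (arm-level failure − observed failure)/unknown: 16.2% and 7.1%.
- Imputed arm rate = observed failure/(observed failure + completed failure-free): 30.1% and 14.1%.

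| | True | Imputed from arm |
|---|---|---|
| Native failure at 36 months | 28.4% | 30.1% |
| Mesh failure at 36 months | 13.2% | 14.1% |
| Difference | 15.3 points | 16.0 points |
| Risk ratio | 0.464 | 0.469 |
| Hazard ratio, ln(1−F mesh)/ln(1−F native) | 0.4226 | 0.4246 |

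Unrounded, the difference grows by 16.02 − 15.25 = 0.76 points. Both ratios move slightly toward the null. With mesh success at 90%, the bottom of the SAP's range, mesh failure goes from 14.6% to about 15.6% and the difference from 13.8 to about 14.5 points.

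**4. At the reported availability.** Loss of 1.4% per year (0.986³ ≈ 0.96) gives a difference of 15.46 against 15.25 points, a shift of about 0.2, and a hazard ratio of 0.4232 against 0.4226.

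**5. Continuous scales (simulation on assumed inputs).** The documents give no within-woman correlations or dropout model. Assumed: correlation 0.6 between 24- and 36-month scores, 0.3 with baseline, no true arm difference, and logistic dropout on the 24-month score with log-odds slope 0.5 to 1.0 per SD. The table gives the spurious arm difference after imputing from baseline and arm.

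| Missing at 36 months | Dependence in one arm only | Opposite in the two arms |
|---|---|---|
| 4% | 0.01–0.02 SD | 0.02–0.04 SD |
| 14% | up to about 0.06–0.07 SD | up to about 0.12–0.13 SD |

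Adding the 24-month score to the imputation model brings the bias to about zero. There is no bias if dropout does not depend on earlier scores. If the dependence is the same in both arms, the biases cancel.

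**The case against.** The strongest objection is that section 7.3 never says 36-month status is imputed. The primary model in 9.3 has one record per woman and period, with later records only while she is at risk. Imputing a missing period indicator there from baseline and arm is already conditional on being failure-free at entry. Under a constant hazard that reproduces the 10.6% and 4.6%. This stands. A reader might infer that the plan assigns a woman failure-free at 24 months the whole 36-month risk; the text permits that reading but does not state it. The defect is that the target is unspecified.

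A reader might also infer that the check would make a positive result look more robust. The documents do not support that: the primary test is of a hazard ratio, and with equal loss that ratio moves slightly toward the null. A larger distortion needs unequal loss. At 10% per year (native) and 5% (mesh) the difference would be 17.9 points, but SAP section 6 plans on "the loss-to-follow-up on both arms is no more than 5% per year".

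Nor is it shown that site is left out. It is fixed at randomization and 7.2 treats it as a covariate, so it may count among the baseline covariates.

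Finally, this is a sensitivity analysis with about 4% missing, and a large imputation model could be unstable with about 87 women per arm and 8 sites. Both points are fair. They limit the size of the problem and the form of the remedy, but do not justify omitting post-operative data.

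**Conclusion.** The concern holds as a specification weakness in a sensitivity analysis that is worth correcting. The stated predictors omit post-operative results that the main models use, so the check cannot do its stated job when dropout depends on those results, and it does not rescue the GEE analyses. For the primary outcome the imputation target is missing. Under the status reading, failure is overstated by 1.7 points (native) and 0.9 points (mesh) at 5% yearly loss, with the hazard ratio essentially unchanged.

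At 96% availability the effect is small: about 0.2 points on the difference, and at most about 0.01 to 0.04 SD on a scale. The primary figures rest on the plan's exponential rates and non-informative loss; the scale figures rest on assumed correlations and dropout slopes.

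Missingness may be larger later. The E-SUPeR amendment expects about 5% fewer women per year through withdrawal or reoperation, and plans methods consistent with the 3- and 5-year analyses. Whether this imputation carries forward is not stated.

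**What to change.** In SAP 7.3, replace the predictor list in "we will use straightforward multiple imputation procedures based on baseline covariates and treatment group" with treatment group, baseline covariates (naming site) and the observed post-operative values of the outcome. Keep the model parsimonious, for example by using the most recent visits only. Add one sentence on the primary outcome: for a woman lost before failure, the remaining time to failure is imputed conditional on being failure-free at her last assessment, and any 12-, 24- or 36-month status is derived from that time.

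The cost is a short SAP edit and a slightly larger imputation model. It needs no new data and does not change the main analyses.
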